The present study will be a single site, prospective, single arm observational study of minimal risk consisting of at least 200 participants who suffer from cold symptoms. The participants must meet additional inclusion/exclusion criteria (see Inclusion/Exclusion Criteria). Participants will begin taking the powder drink-mix at the onset of their cold symptoms. Onset is defined as the point in time the participant experiences 2 or more cold symptoms (cough, hoarseness, muscle ache, nasal drainage,

nasal congestion, scratchy throat, sore throat, sneezing, or an oral temperature greater than 37.7 °C (99.9 °F)). When the participant experiences 2 or more symptoms, they will report symptoms in the cold start form. If they meet the criteria for a cold, they will start completing the daily cold symptom diary prior to taking the test product. After consuming the product, the participant will complete the cold symptom diary daily until all symptoms resolve. Since none of the ingredients in the test product have been seen to provide relief from fever or pain, the participant will be allowed to take a pain reliever and fever reducer (e.g. ibuprofen or acetaminophen). If medication is taken, the participant will record this in their symptom diary.

Study enrollment and management will be decentralized, where participants do not visit an investigator or a clinic for clinical assessment. The participants will participate in the study at home. All data collected from during this study will be reported by the participant via eCRFs, eDiary, and other electronic data entries. If a visit is required, it will be conducted via remote contact by telephone.

4.1.Test Product

Overview:

Participants in this study will consume the test product twice a day (4-6 hours apart) at the onset of cold symptoms. The participant will mix one packet of the test product in 6-8 ounces of water. The test product will be delivered to the participants' residence in a single shipment consisting of an18-day supply (36 packets) of the test product. The study participant will mix the contents of the packet into 6-8 oz. of hot water and drink twice a day during the duration of the cold.

Below is the description of the test product and its ingredients.

Test Product

Description: Combining whole food sourced Vitamin C, Echinacea, Ivy Extract, Zinc, Ginger and Turmeric. This formula is designed to support the immune system while reducing the duration of cold.

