4.3. Participation Period

Participants are expected to participate in the study for 18 days after the onset of the first cold. Onset is defined as the day that the participant experiences 2 or more cold symptoms. Participant will be exited once all symptoms have been resolved or at 18 days whichever is shorter. If no cold has started within 90 days of participant study start date (date the participant receives and records receipt of test product) participants will be exited from the study.

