- Participant will take the test product twice a day, at least 4-6 hours apart.
- The next day the participant will complete their symptom diary prior to taking the test product. Once completed they will mix 1 packet of the test product into 6-8 oz of water and consume the whole drink. They will take the test product again 4-6 hours later.
- The participant will complete this process daily until their cold symptoms resolve or for 18 days, whichever is shorter.
- If the participant takes ibuprofen or acetaminophen at any time, the participant will record this on their symptom diary.
- After taking the test product, the participant will be instructed to fill out an Adverse Event form for any side-effects experienced.
- The participant will be prompted, by email, to complete the study exit form once the participant's symptoms resolve completely or after 18 days, whichever is shorter.
- Neither the sponsor nor Hawthorne Effect, Inc. will make any attempt to collect any unused test product.
- Upon receipt of study exit survey and review of completed study forms, participant will receive an Amazon gift card of \$25 via email.

6.2.Study Schedule of Activities

Assessments	Screening	Consent	Before Receipt of Test Product	Product Received	Event Start Date**	Days 1-18*	Study Exit***
Study Window							
Screening Survey	Х						
Consent		Х					
Baseline Survey			х				
Demographics			х				
Acknowledgement of Receipt of Test Product				Х			
Test Product Consumed****					Х	Х	
Symptom Diary					Х	Х	Х
Meds & Supplements			Х				
AE Assessment					Х	Х	Х
Study Exit Survey							Х

^{*}Participant will participate in the study starting on the day of the cold until the cold symptoms resolve or 18 days whichever is shorter.

^{**} The day the participant experiences 2 or more of the protocol defined symptoms

^{***} The participant will exit the study at the time of complete cold symptom resolution, 18 days after the start of cold symptoms, or at 90 days if no cold is experienced by the participant.

^{****} The product will be consumed twice a day, 4-6 hours apart

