7.1. Study Outcomes Measures

Analysis populations:

The *intent to treat* (ITT) population consists of all participants who are consented, report the onset of cold symptoms, and have taken the test product at least once. The primary analysis will be in the ITT population.

Primary Endpoint:

• The primary endpoint will be time to freedom from cold symptoms, with the clock starting at the onset of the cold. Where the onset is defined as the point in time when the participant experiences 2 or more cold symptoms. The primary analysis will be a Kaplan-Meier analysis of time to absence of all symptoms, based on the participant's self-report. There is no control group for the primary analysis.

Secondary Endpoints:

- Secondary endpoints involve the duration and severity of the separate cold symptoms.
- Comparison against the participant's normal behavior.
- Net Promoter Score.
- Adverse events will be summarized.
- An additional data presentation will consist of results from both Treatment and Control in similar studies appearing in the literature. There will be no formal statistical comparison of results from this study and historical studies.

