7.3. Analysis Plan

Time-dependent variable analysis

The primary analysis involves time dependent variables. The Kaplan-Meier algorithm will be used to analyze time to freedom from cold symptoms. Data presentation will include tables and graphs; in particular tables of participants at risk at various time points.

Censoring:

- Participants who do not have a cold during the trial will not be in the ITT population, and will
 not be included in the endpoint analysis.
- Participants who report the onset of a cold, but who do not complete the daily reports through
 18 days will be censored as of the date of the last report.
- Participants who still have cold symptoms at 18 days will be censored at that time.
- Participants will also be censored if they withdraw from the trial.

Secondary Endpoints:

- Analysis of the individual cold symptoms will be a presentation of median time until the
 individual symptom resolves. The median for this purpose is the value computed as part of
 the Kaplan-Meier algorithm.
- An additional analysis will investigate the relation between baseline age and gender, and the time to resolution.
- Adverse events will be summarized.
- An additional data presentation will consist of side by side presentation of results from both

Treatment and Control in similar studies appearing in the literature. There will be no formal statistical comparison of results from this study and historical studies.

General statistical methods:

Data will be analyzed using standard statistical methods, as further specified in a statistical analysis plan (SAP), which will be prepared in detail at a later date. [23]

- Data analysis will largely consist of summary statistics and graphs. The only formal statistical comparisons will be in covariate analyses.
- For continuous variables data presentation will consist of means, confidence intervals computed using the *t*-statistic, medians, and interquartile ranges. Group comparisons will use *t*-tests or ANOVA.
- For discrete variables confidence intervals will use the exact intervals, where available. Group comparisons will use Fisher's exact test, with the Monte Carlo version used where computationally necessary.
- For time to event variables analysis will use the Kaplan-Meier algorithm, and group comparisons will use the log-rank or proportional hazards methods, depending on the data type.
- Covariate analyses will investigate the relation between baseline and outcome variables, using

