 methods appropriate to the data types involved. Age, gender, and baseline medications will be
 included in these analyses where appropriate data are available.
- Present intention is that the analysis will be performed in R, and the precise form of algorithms will be the default of R. Kaplan-Meier, log-rank, and proportional hazards algorithms will be the defaults of the survival package.
- Visual analog scale values will be treated as continuous variables. Frequency counts will also be provided for scales with 10 or fewer distinct response levels.
- The exact items to be compared depend on what is reported in each historical control study. When possible, the items will include time to resolution of all cold symptoms, time to resolution of each individual cold symptom, proportion of cold symptoms resolved at each time, and reported baseline characteristics. When two-arm studies are compared, both arms will be reported in this comparison. Specific studies to be considered will include the Cleveland study, and other studies identified prior to the analysis of actual trial data.

8.Informed Consent Process

The study protocol and informed consent will be reviewed and approved by Advarra Institutional Review Board prior to study start.

Study candidates will learn about the study via digital advertisements. If interested in learning more, they will be referred to a website "landing page" that will provide detailed information about the study. They may opt to complete a screening survey ascertaining study eligibility through patient reported outcomes. If successfully completed (no exclusion criteria are selected), candidate will be invited to review the study consent form tutorial which includes the opportunity to ask questions related to the study from the Principal Investigator or delegated authority of the investigator. Candidate will be proved with contact information to reach investigator or study manager as desired.

Candidate may sign the informed consent via electronic signature as provided by Hawthorne Effect. The study manager will verify candidate signature prior to enrollment as a study participant.

9. Subject Confidentiality

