13.1.5. Appendix E Symptom Diary

Daily Symptom Survey

BEFOREtaking the test product OR any allowed medication, please answer all of the following questions daily for the duration of your cold symptoms.

REMINDER: DURING THE TRIAL, YOU ARE NOT ALLOWED TO TAKE ANY COLD MEDICATIONS (NYQUIL/DAYQUIL, TYLENOL COLD, COUGH SYRUP/LOZENGES, ETC.)

1. Cough			
0	1	2	3
No Symptom	Slight	Moderate	Severe
2. Hoarseness			
0	1	2	3
No Symptom	Slight	Moderate	Severe
3. Muscle aches			
0	1	2	3
No Symptom	Slight	Moderate	Severe
4. Runny Nose			
0	1	2	3
No Symptom	Slight	Moderate	Severe
5. Nasal Congestion			
0	1	2	3
No Symptom	Slight	Moderate	Severe
6. Scratchy Throat			
0	1	2	3
No Symptom	Slight	Moderate	Severe

7. Sore throat

0	1	2	3
No Symptom	Slight	Moderate	Severe
8. Sneezing			
0	1	2	3
No Symptom	Slight	Moderate	Severe

- 9. Did you take any pain/fever reducer (ibuprofen/acetaminophen today? (Y/N)
 - a. Why?
 - b. Did it work? (Y/N)
- 10. Have you taken any other cold medications (Nyquil, Dayquil, other cold medication, cough drop, cough syrup, etc.)? (Y/N)
 - a. If yes, please exit from the study
- 11. Have you seen a doctor for your symptoms? (Y/N)
 - a. If yes, were you prescribed anything? $(Y/N) \rightarrow$ if yes please exit from the study
- 12. Did you experience any side effects after taking the product? (Y/N)
 - a. If yes, please fill out the Adverse Event form.

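### Symptom severity is a secondary endpoint with no stated analysis, and because diaries stop at recovery the default daily summaries would lean toward participants still ill

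*Combined protocol and SAP*

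**What the plan says.** **Endpoint.** Section 7.1: "Secondary endpoints involve the duration and severity of the separate cold symptoms". The synopsis and sections 3 and 4.4 say the same in substance.

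**Data.** Appendix E scores eight symptoms from 0 to 3. Participants are told to "answer all of the following questions daily for the duration of your cold symptoms".

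**When recording stops.**
- Section 4: "After consuming the product, the participant will complete the cold symptom diary daily until all symptoms resolve".
- Section 6.1: "The participant will complete this process daily until their cold symptoms resolve or for 18 days, whichever is shorter".
- Section 4.3: "Participant will be exited once all symptoms have been resolved or at 18 days whichever is shorter".
- The schedule in section 6.2 also marks a symptom diary at study exit, so the all-zero diary on the day of recovery can be captured.

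**Analysis.** Section 7.3: "Analysis of the individual cold symptoms will be a presentation of median time until the" individual symptom resolves, taken from Kaplan-Meier. That covers duration. For severity only the general methods remain: "For continuous variables data presentation will consist of means, confidence intervals computed using the" t-statistic, with medians and interquartile ranges, plus frequency counts for scales with ten or fewer levels. The literature display may include the "proportion of cold symptoms resolved at each time", with no denominator given. Further detail is deferred to a SAP still to be written.

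**The concern.** A participant who recovers on day 5 has no severity score on days 6 to 18. Those days are not missing in the usual sense: the participant is known to have been symptom-free at exit. If each day is summarised over the diaries received, the best outcomes drop out and the remaining group becomes smaller and sicker day by day. Mean severity is then too high, and each day's t interval describes a different, selected group.

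At stake are a named secondary endpoint and the literature display. Section 7.2 wants a reasonable comparison with the zinc lozenge trial. A series based on those still reporting cannot be set fairly beside one that keeps recovered patients in its denominator. In a single-arm study where everyone knows the treatment, this choice should not be left until the data are in hand.

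**Working it through.** **1. The plan's own figure.** Section 7.2 expects 40% of 200 enrolled participants to have a cold: 200 × 0.40 = 80, which reproduces. The documents state no severity mean or proportion resolved, so there is no figure on this point itself to reproduce.

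**2. Which records exist.** Before complete recovery all eight items are recorded daily, so a symptom that clears early is scored 0 while others persist. On the recovery day an all-zero diary is possible (section 6.2). After that there is nothing. No text assigns a score to those later days.

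**3. The relation that drives the bias.** If recovered participants truly score 0 and nobody drops out, then

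mean over diaries received = mean over all treated ÷ share of treated with a diary that day.

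The inflation factor is one over the share still reporting, so it grows with time.

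**4. Illustration A (total score).** Assumptions, none from the documents: Weibull time to recovery D with median 7 days and shape 1.8; total score on day d of 1 + 7 × (1 − d/D) while ill and 0 afterwards; D rounded up to whole days; no exit-day diary.

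| Day | Still ill | Mean, still ill | Mean, all treated |
|---|---|---|---|
| 3 | 86% | 5.22 | 4.49 |
| 5 | 69% | 4.18 | 2.87 |
| 7 | 50% | 3.48 | 1.74 |
| 10 | 27% | 2.79 | 0.75 |

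Check: 0.50 × 3.48 = 1.74 and 0.27 × 2.79 = 0.75.

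Now keep the exit-day zero diary, with D left continuous. The Weibull scale is 7 ÷ (ln 2)^(1/1.8) = 8.58. The share with a diary on day d is the share still ill on day d − 1:
- Day 7: exp(−(6/8.58)^1.8) = 0.592. Mean on diaries received is 1.619 ÷ 0.592 = 2.73, against 1.62 over all.
- Day 10: exp(−(9/8.58)^1.8) = 0.337. Mean on diaries received is 0.690 ÷ 0.337 = 2.05, against 0.69 over all.

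The gap shrinks but stays large.

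**5. Illustration B (per symptom, 0-3, N = 80).** Assumptions: lognormal duration with log-SD 0.5; eight symptoms ending at or before the overall end; starting scores 1 to 3 falling linearly; last diary is the first all-zero one; no dropout; 1,500 simulated trials. Each cell gives diaries received / all 80 with zeros after recovery.

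| | Median 4 d | Median 6 d | Median 8 d |
|---|---|---|---|
| Diaries on day 7 | 17 of 80 | 40 of 80 | 57 of 80 |
| Day 7 mean severity | 0.29 / 0.06 | 0.43 / 0.22 | 0.58 / 0.42 |
| Day 7 proportion of symptoms resolved | 0.73 / 0.94 | 0.62 / 0.81 | 0.51 / 0.65 |
| Day 10 mean severity | 0.26 / 0.01 | 0.35 / 0.07 | 0.44 / 0.18 |
| Day 10 proportion of symptoms resolved | 0.75 / 0.99 | 0.68 / 0.93 | 0.61 / 0.84 |

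**6. Is improvement lost or only understated?** With a median of 6 days, the mean on diaries received falls from 0.966 on day 3 to 0.432 on day 7, a drop of 0.534. Over all 80 it falls from 0.952 to 0.216, a drop of 0.736. The diary-based series shows 0.534 ÷ 0.736 = 73% of the improvement: understated, not absent.

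**The case against.** **The plan prescribes no daily severity mean.** It is silent on the summary, the time points and the denominator. A reader might infer that severity will be computed only on people still ill. No passage says so, and the later SAP could choose well. This stands, and the point is worded accordingly. But the only summaries on offer, applied by day to the records the design produces, give the biased answer, and no text prevents that.

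**Means and t intervals may not govern four-level items.** Frequency counts or the rule for discrete variables might apply instead. True, but counts over the diaries received have the same shrinking denominator.

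**The proportion resolved need not be biased.** A reader might infer that it shares the defect. The documents do not establish that: one minus the Kaplan-Meier estimate, a method section 7.3 already names, counts recovered participants as events. The item is also conditional on what each historical study reports. What stands is that its denominator should be stated.

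**Improvement is hidden.** This too can be inferred, but step 6 shows a falling series.

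**The primary result is at risk.** It is not, by this mechanism: resolution is the Kaplan-Meier event. Read literally, the 7.3 rule that censors anyone not reporting through day 18 would catch recovered participants, but that is a separate wording conflict with exit at resolution.

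**Scoring zeros does not settle early exits.** Section 4.2 exits participants who take cold remedies or are prescribed medication. They are plausibly the sicker ones; a denominator of those not yet censored could bias severity downward, and an area to day 18 is undefined for them. This stands and is addressed in the fix.

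**Conclusion.** The concern holds as an unspecified analysis whose available defaults would mislead. Severity is a named secondary endpoint, section 7.3 analyses only duration, and recording stops at complete recovery. Daily summaries of the diaries received would overstate later severity and understate improvement.

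The direction follows from the design, provided recovered participants remain well. The size does not: it depends on the assumed distribution of cold duration and course of symptoms, for which the documents give no figures. In both illustrations the day-7 mean is inflated at every assumed median and the relative gap is wider by day 10. In illustration B the day-7 ratio runs from about 1.4 (0.58 ÷ 0.42) to about 4.8 (0.29 ÷ 0.06).

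The consequence is confined to descriptive secondary results and the informal literature display. It should be fixed before the data are analysed.

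**What to change.** In section 7.3, carried into the SAP:

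1. **Post-recovery days.** Score all eight items 0 from the documented day of complete resolution through day 18. Keep missing days before recovery as missing, not 0.
2. **Denominator.** For each day use all ITT participants not yet censored, with recovered participants retained.
3. **Severity summary.** Name one per symptom, for example the mean daily score or the area under the score over days 1-18. State how participants who leave early for prohibited medication or by withdrawal are handled, with a sensitivity analysis.
4. **Proportion resolved.** For each symptom and time, use 1 minus the Kaplan-Meier estimate.
5. **Censoring rule.** Limit censoring at the last report to participants who stop reporting without having reported resolution, so that it agrees with exit at resolution in sections 4.3 and 6.1.

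**Cost.** A few sentences and a few lines of code, with no new data. The price is an assumption that nobody relapses after exit. The diary cannot test it, so it should be stated beside the results.

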7.2. Sample Size Considerations

The referenced paper of Mossad, Macknin, et al. had a sample size of 100 patients with colds, of which 50 were in the treatment arm. Based on informal readings of various sources, we estimate that approximately 40% of the enrolled participants in this trial will experience a cold during the 90-day period. A sample size of 200 enrolled participants would then yield 80 participants with colds. Even with the uncertainties of compliance in this trial, the sample size should enable reasonable comparison of results against the Mossad, Mackin et al. study. [20]

As discussed above, the number 200 may be increased based on observed data concerning the number of participants with colds. The actual outcomes of treated participants will not be considered in this analysis, merely whether or not enrolled participants have reported starting using the test product. The method of reevaluating the sample size will be described in the Statistical Analysis Plan.

7.3. Analysis Plan

Time-dependent variable analysis

The primary analysis involves time dependent variables. The Kaplan-Meier algorithm will be used to analyze time to freedom from cold symptoms. Data presentation will include tables and graphs; in particular tables of participants at risk at various time points.

Censoring:

- Participants who do not have a cold during the trial will not be in the ITT population, and will
 not be included in the endpoint analysis.
- Participants who report the onset of a cold, but who do not complete the daily reports through
 18 days will be censored as of the date of the last report.
- Participants who still have cold symptoms at 18 days will be censored at that time.
- Participants will also be censored if they withdraw from the trial.

Secondary Endpoints:

- Analysis of the individual cold symptoms will be a presentation of median time until the
 individual symptom resolves. The median for this purpose is the value computed as part of
 the Kaplan-Meier algorithm.
- An additional analysis will investigate the relation between baseline age and gender, and the time to resolution.
- Adverse events will be summarized.
- An additional data presentation will consist of side by side presentation of results from both

Treatment and Control in similar studies appearing in the literature. There will be no formal statistical comparison of results from this study and historical studies.

General statistical methods:

Data will be analyzed using standard statistical methods, as further specified in a statistical analysis plan (SAP), which will be prepared in detail at a later date. [23]

- Data analysis will largely consist of summary statistics and graphs. The only formal statistical comparisons will be in covariate analyses.
- For continuous variables data presentation will consist of means, confidence intervals computed using the *t*-statistic, medians, and interquartile ranges. Group comparisons will use *t*-tests or ANOVA.
- For discrete variables confidence intervals will use the exact intervals, where available. Group comparisons will use Fisher's exact test, with the Monte Carlo version used where computationally necessary.
- For time to event variables analysis will use the Kaplan-Meier algorithm, and group comparisons will use the log-rank or proportional hazards methods, depending on the data type.
- Covariate analyses will investigate the relation between baseline and outcome variables, using
 methods appropriate to the data types involved. Age, gender, and baseline medications will be
 included in these analyses where appropriate data are available.
- Present intention is that the analysis will be performed in R, and the precise form of algorithms will be the default of R. Kaplan-Meier, log-rank, and proportional hazards algorithms will be the defaults of the survival package.
- Visual analog scale values will be treated as continuous variables. Frequency counts will also be provided for scales with 10 or fewer distinct response levels.
- The exact items to be compared depend on what is reported in each historical control study. When possible, the items will include time to resolution of all cold symptoms, time to resolution of each individual cold symptom, proportion of cold symptoms resolved at each time, and reported baseline characteristics. When two-arm studies are compared, both arms will be reported in this comparison. Specific studies to be considered will include the Cleveland study, and other studies identified prior to the analysis of actual trial data.

8.Informed Consent Process

The study protocol and informed consent will be reviewed and approved by Advarra Institutional Review Board prior to study start.

Study candidates will learn about the study via digital advertisements. If interested in learning more, they will be referred to a website "landing page" that will provide detailed information about the study. They may opt to complete a screening survey ascertaining study eligibility through patient reported outcomes. If successfully completed (no exclusion criteria are selected), candidate will be invited to review the study consent form tutorial which includes the opportunity to ask questions related to the study from the Principal Investigator or delegated authority of the investigator. Candidate will be proved with contact information to reach investigator or study manager as desired.

Candidate may sign the informed consent via electronic signature as provided by Hawthorne Effect. The study manager will verify candidate signature prior to enrollment as a study participant.

9. Subject Confidentiality

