2.2.3. Minimization of Risks

Research participants will be carefully screened to meet enrollment criteria. Participants meeting exclusion criteria will not be enrolled. The study participant informed consent will be presented with clear description of the study requirements and opportunity to have questions answered before enrollment will be provided. Once an event occurs, review of symptoms will be

ascertained daily until symptoms have resolved or for 18 days. Reporting of adverse events will be reviewed routinely and in accordance with regulatory guidelines (21CFR, GCP) by the Principal Investigator. Participants with occurrence of worsening symptoms or adverse events will be advised to stop the product and may seek medical attention and exit the study.

3. Study Objectives

The purpose of the present study is to evaluate 1) the impact of the Immune Support test product on the duration of symptoms of the common cold in adult participants and 2) the subjective experience of these participants related to general health, common cold symptoms, and personal experience with the product. [13, 18, 29, 32]

This will be evaluated based on the primary and secondary endpoints. These endpoints, the analysis populations, and their respective measures are described below. Further details on the methods for measuring the outcomes can be found in the Study Outcome Measures and Analysis Plan sections.

Primary Endpoint:

The primary endpoint will be time to freedom from cold symptoms, with the clock starting at the onset of the cold. Where the onset is defined as the point in time when the participant experiences 2 or more cold symptoms. The primary analysis will be a Kaplan-Meier analysis of time to absence of all symptoms, based on the participants' self-report. There is no control group for the primary analysis. [5]

Secondary Endpoint:

- Secondary endpoints involve the duration and severity of the separate cold symptoms.
- Comparison against the participant's normal behavior.
- Net Promoter Score.
- Adverse events will be summarized.
- An additional data presentation will consist of results from both Treatment and Control in similar studies appearing in the literature. There will be no formal statistical comparison of results from this study and historical studies.

4.Study Design

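### The second censoring rule in Section 7.3, read literally, censors everyone who recovers before day 18; recovery should be stated to come first

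*Combined protocol and SAP*

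**What the plan says.** Section 7.1 sets the endpoint: "The primary analysis will be a Kaplan-Meier analysis of time to absence of all symptoms". Section 7.3 then lists the censoring rules. The first keeps participants without a cold out of the analysis. The other three are:

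- Rule 2 covers "Participants who report the onset of a cold, but who do not complete the daily reports through" day 18; their final report supplies the censoring date.
- Rule 3: "Participants who still have cold symptoms at 18 days will be censored at that time".
- Rule 4: "Participants will also be censored if they withdraw from the trial".

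Reporting is designed to be shorter than 18 days for most people. Section 2.2.3 has symptoms "ascertained daily until symptoms have resolved or for 18 days". Section 4 says "the participant will complete the cold symptom diary daily until all symptoms resolve". Section 4.3 exits participants at resolution or day 18, whichever comes first, and Section 6.1 ends the daily process at the same point. Appendix E asks for entries only while symptoms last, although the Section 6.2 schedule also marks a symptom diary at study exit.

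The individual symptoms are handled by the same method: "Analysis of the individual cold symptoms will be a presentation of median time until the" symptom resolves, with the median taken from Kaplan-Meier.

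**The concern.** Rule 2 turns on whether daily reports run through 18 days, not on whether the participant has recovered. A participant who does as asked and recovers on day 7 has no reports for days 8 to 18, and so meets the censoring condition. The same observation is the event under Section 7.1 and a censored time under rule 2. Nothing in the documents says which prevails. Rule 4 is also silent on a withdrawal that follows a recorded recovery.

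At stake is the status variable of the sole primary analysis. Section 7.3 leaves the detailed SAP to a later date. If that SAP copies rule 2, the error goes with it.

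Two gaps in the diary form bear on how the event is recognised. Appendix E does not clearly ask for the symptom-free entry that would mark recovery. It also scores eight symptoms, whereas Section 4 lists nine. The missing one is raised oral temperature, which Section 6.1 says is recorded in the diary. An all-zero diary therefore does not quite show that all listed symptoms are absent.

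**Working it through.** **The plan's own figure.** Section 7.2 expects 40% of 200 enrolled participants to have a cold: 200 × 0.40 = 80. This reproduces. The plan states no power, effect size or expected median, so there is nothing further to reproduce.

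**Rule 2 applied to one participant.** Recovery and last report both fall on day 7.
- Section 7.1: symptoms absent on day 7, so event at day 7.
- Rule 2: reports do not run through day 18, so censored at day 7.
- Rule 3: does not apply, because the participant is not still ill at day 18.

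The same holds for any recovery day before 18.

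**Rule 2 applied to the curve.** The estimate is S(t) = ∏(1 − d_j/n_j), where d_j is the number of events and n_j the number at risk on day j. If every recovery before day 18 is censored, d_j = 0 for every j up to 17. Each factor is then 1 and S(17) = 1.00. No recovery distribution enters this result.

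As an illustration, suppose 40 of the 80 recover by day 7 and nobody else has been censored by then. With recovery as the event, S(7) = 40/80 = 0.50. Under rule 2 as written, S(7) = 1.00.

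**Scale of the difference.** Kaplan-Meier was simulated with n = 80 and 2,000 runs per scenario. The assumptions, none from the documents, were Weibull recovery times with median 4 to 10 days and shape 1.0 to 2.0, and dropout unrelated to recovery of 0%, 10% or 20% over 18 days.

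| Quantity | Event first | Rule 2 as written |
|---|---|---|
| Mean number of events before day 18 | about 51 to 80 | 0 in every scenario |
| Mean number of events on day 18 | about 0 to 2.4 | about 0 to 2.4 |
| Kaplan-Meier median | about 4.5 to 10.7 days | not estimable in at least about 66% of runs in every scenario; day 18 when it exists |

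Event-first coding recovers the assumed median up to daily rounding.

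**Diary against the symptom list.** Section 4 lists cough, hoarseness, muscle ache, nasal drainage, nasal congestion, scratchy throat, sore throat, sneezing and raised temperature: nine. Appendix E scores the first eight (drainage appears as runny nose): 9 − 8 = 1 listed symptom unscored.

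**The case against.** The best defence is that no competent analyst would apply rule 2 this way. In a Kaplan-Meier analysis, censoring concerns people who have not had the event. Section 7.1 names the event, and rule 3 censors at day 18 only those still ill, which makes sense only if recovery by then counts. Since Section 6.1 ends the daily process at recovery, someone who reported until then has arguably completed the daily reports. The SAP could settle the rest.

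Most of this stands. A reader might infer that the documents give no way out of the conflict, or that the trial would really publish a flat curve. Neither is supported: the endpoint and rule 3 point clearly to recovery as the event. What does not stand is that the text already says so. Rule 2 names 18 days, and reading that as 18 days or recovery adds words that are not there.

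A reader might also infer that skipped final entries seriously lengthen the estimated duration. The documents give no skip rate. The exit diary in Section 6.2, the reminders, the exit prompt and the gift card released after review of the forms all work against it. Withdrawal after a recorded recovery should likewise be rare, because Section 4.3 exits people at recovery.

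**Conclusion.** The point holds as a contradiction in wording. Rule 2 conflicts with the primary endpoint, with rule 3 and with the reporting procedures. Taken literally it leaves 0 events before day 18 and a curve at 1.00 through day 17. That result assumes only that participants stop reporting at recovery, as instructed; anyone who kept reporting through day 18 would escape the rule. The event counts and medians under event-first coding depend on the assumed recovery times and dropout.

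It is a drafting error that would probably be coded around, and it does not show that the eventual results will be wrong. It should still be corrected before the SAP is written, because it is the stated rule for the only primary analysis and correcting it costs almost nothing. The form gaps are secondary, and the documents give no basis for putting a size on them.

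**What to change.** Replace rule 2 with: *The event is the first daily report with all symptoms absent, on or before day 18. Participants without an event whose daily reports stop before day 18 are censored at the date of the last report.*

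Add that rules 3 and 4 apply only to participants with no earlier event. State the same event-first order for the individual-symptom medians, and carry all of it into the SAP.

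In support, change Appendix E in two places. Ask for one final entry with every symptom scored 0, in line with the exit diary in Section 6.2. Add the temperature entry that Section 6.1 already expects there.

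The cost is two or three sentences in Section 7.3, one instruction line and one diary item. Treatment, visits and sample size are unaffected.
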